7. SOURCES OF RESEARCH MATERIAL

Skin Biopsy

4 mm punch biopsies (three; affected-treated, affected-untreated, and unaffected skin) of up to 15 patients will be performed under local anesthesia by an investigator who has been formally trained to perform a skin biopsy. The biopsies will be performed using standard sterile technique. Skin will be closed with a single 3-0 or 4-0 polypropylene or nylon suture. These biopsies will take place during Study Visits 1 and 3 during a scheduled research-only clinic visit. The investigator will avoid cosmetically sensitive areas such as the face for biopsies, unless the patient permits.

Blood

Approximately 40 cc of blood will be collected from a vein in the subject's arm at the Study Visits during a scheduled research-only clinic visit by a support staff person or an investigator who has been formally trained to conduct venipuncture.

Patient Data

Other data used in the research will be obtained from the subjects' medical records and in-person interviews. The data sought will include the subject's age, gender, race, age of diagnosis, contact information, disease location, presentation and history, associated symptoms, past and current treatments, personal history of autoimmune diseases, family history, and quality of life assessments. At return study visits, subjects will update the investigators on changes to their disease history, associated symptoms, treatments, quality-of-life assessments, and will be assessed for adverse events. At each Study Visit, an investigator will perform a skin examination, obtain severity index scores for cutaneous and systemic lupus (i.e. CLASI, SELENA-SLEDAI), provide physician's assessment of disease activity, and obtain photographs.

8. LABORATORY PROCEDURES

Differences in gene expression before and after UVA1 treatment may yield insight into possible mechanisms of action for UVA1 treatment in cutaneous lupus. To investigate expression of individual genes, DNA and RNA testing will be conducted on both blood and skin samples. Planned experiments include microarray analyses to generate global expression patterns of multiple genes and RT-PCR for verification of gene expression. Skin biopsy and blood samples may also be used for assessment of protein expression using immunohistochemistry and flow cytometry, respectively.

9. RECRUITMENT

A total of 15 patients will be recruited from the University of Texas (UT) Southwestern Medical Center at Dallas (Professional Office Building 1 Dermatology Clinic), the already established UT Southwestern Cutaneous Lupus Registry (IRB #082010-241, "Molecular Studies in Cutaneous Lupus") and the Parkland Health and Hospital System (Parkland Dermatology Clinic). To date, >150 cutaneous lupus patients have been recruited to the UT Southwestern Cutaneous Lupus Registry. Referring physicians will be asked to discuss the study with prospective participants. If they are interested, the physician can provide the study center's contact information. The study coordinator/doctor will explain the purpose of the study, length of the study, procedures involved in the study, and the risks/benefits of the study to prospective participants either in person or by telephone. After all questions have been answered and the participant agrees to participate the consent form will be signed. Based on current practice in our center, we anticipate completing enrollment within the first two years of the study.

During the recruiting and consenting process, the investigators will adhere to UT and Food and Drug Administration (FDA) guidelines. The purpose, the duration, the procedures (blood and skin biopsy sample collections), and the risks/benefits of the study will be explained to each potential subject by the investigators. Subjects will be given a copy of the consent form and Health Insurance Portability and Accountability Act (HIPAA) authorization to read. They will be given ample time for questions and answers to their questions by the investigator. The signed consent and HIPAA forms will be kept in secure files by the investigators, and copies will be given to the subjects. The collection of study samples will not start until the subject signs the consent and HIPAA forms. (*Note: This is in addition to the consent form and post-biopsy instructions given to the subjects for skin biopsy.*)

10. TRAINING IN THE POLICES PROTECTING THE RIGHTS AND WELFARE OF HUMAN SUBJECTS IN RESEARCH

All the investigators have completed their Human Subjects Protections training and HIPAA training in compliance with UT Southwestern policies and procedures. They will adhere to the UT and the FDA guidelines while conducting this research project to assure study integrity.

11. POTENTIAL RISKS

UVA1 light treatments: There are several potential risks of ultraviolet light exposure:

Short-term risks:

- Marked hyperpigmentation or tanning, erythema, pruritus, photosensitive eruptions, and recrudescence of herpes simplex infection (HSV).
- Flaring of lupus disease, which may include having new skin lesions, increased fatigue, and joint pains.

Long-term risks:

- The most common is aging of the skin: Repeated and prolonged exposure to ultraviolet light induces changes in the skin, which appear as premature aging. These include thinning and wrinkling of the skin in addition to freckling.
- Less common is injury to eyes: Ultraviolet light can injure the subject's eyes. Subjects will be required to wear protective eye shields (goggles) at all times during their UVA1 treatments.
- Rare is skin cancer: Repeated and prolonged exposure to ultraviolet light can increase the subject's risk of skin cancer. This includes exposure from natural sunlight, UVB phototherapy, PUVA or tanning salons. Actinic keratoses (sun-damage spots) can also occur with any long-term exposure to ultraviolet light. Only one case report of UVA1-treated patients developing skin cancers has been reported.¹⁵
- The risk of skin cancer is particularly increased in the genital area, especially in men. Because of this, subjects must shield the genital areas during each treatment

Biopsy: The most common side effects associated with biopsies of the skin are pain at the site, bleeding, bruising at the site, scarring at the site and infection at the site.

Sample of blood: The patient may experience discomfort, bleeding, and/or bruising. The patient may feel dizzy or faint. On a rare occasion, an infection could develop at the site where the blood was collected.

Stress: The patient could experience stress from participating in this kind of research. Knowing that researchers have personal information about them may trouble the patient.

Loss of confidentiality: It is possible that identifiable health information may be accidentally shared and subject confidentiality is lost. Every effort will be made to make sure the subject's information is kept confidential (including the covering of tattoos, birthmarks, etc. in photographs in order to conceal the subject's identity).

12. SUBJECT SAFETY AND DATA MONITORING

Subject safety: Goggles will be worn at all times by the patient during UVA1 phototherapy. The patient will apply sunscreen to nipples/areolas and cover genitals. A symptom questionnaire assessing symptoms of lupus flare, photosensitivity, and changes in medications will be provided at the initial phototherapy orientation. Participants will be asked to review this at home prior to each UVA1 treatment session. This questionnaire will also be reviewed before each UVA1 treatment session by the phototherapy nursing staff. Patients will be assessed for erythema by phototherapy nursing staff prior to UVA1 treatment. Any observed erythema will be reported to the PI. Furthermore, suggestion of a lupus flare on the questionnaire will trigger immediate reporting to the PI prior to any further treatment. If a flare is verified based on investigator assessment, the patient will be withdrawn from the study. A lupus flare will be defined by having an increase in the SELENA-SLEDAI score of at least three. In the event of photosensitivity reported on the questionnaire, the PI will be notified and will evaluate the patient. If a reported reaction is deemed to be sunburn-type erythema, the dose of UVA1 will be decreased to 6 J/cm² and held at that dose throughout treatment. If symptoms persist, the patient will be withdrawn from the study. The patient's medications will always be reviewed prior to initiation of UVA1 phototherapy, but no dose change will be instituted for photosensitizing medications, given the low dose of UVA1 in this study. UVA1 light can induce HSV (cold sores) especially if the patient has a personal history. If this occurs, the PI will be notified for treatment and possible prophylaxis.

Local anesthetic is used before a skin biopsy procedure. In both the blood draw and the biopsy, guidelines are used for a sterilized procedure. All personnel performing biopsies and phlebotomy are fully trained with experience.

In the event of a patient experiencing stress from participating in this type of research, referrals for the proper counseling will be available.

Data Monitoring: All identifiable information will be kept in separate data logs and data tables. Subject specimens and samples will be labeled with unique identifiers with no identifiable information on them. Data will not be shared with investigators outside the ones listed on this project summary, yet, if shared, this data will be de-identified.

Data Safety and Monitoring Plan: The PI ([name]) will be solely responsible for the data and safety monitoring. Data to be monitored includes: study accrual rate, experience of study participants, study attrition including participant withdrawals/dropouts, pattern of adverse events and/or unanticipated events, patterns of protocol deviations and/or violations, and changes in risk/benefit. Frequency of data monitoring and analysis will occur quarterly.

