4. ELIGIBILITY CRITERIA

Criteria for Inclusion of Participants

1. Age > 18 years at enrollment.
2. Diagnosis of cutaneous lupus confirmed by clinicopathological correlation.
3. CLASI activity score of ≥ 2 .
4. Stable dose of antimalarials (hydroxychloroquine, quinacrine, or chloroquine) for 60 days.
5. Stable dose of immunosuppressive medications (e.g. mycophenolate mofetil, methotrexate, low dose prednisone <10 mg daily) for at least 30 days.
6. Stable use of topical medications including steroids (e.g. triamcinolone, clobetasol) and steroid-sparing agents (e.g. tacrolimus) for at least 30 days.
7. Patient must be able to speak and read English or Spanish at a 6th grade reading level. A translator will be available with additional consent forms in Spanish.
8. All races, ethnic backgrounds, and genders will be eligible.
9. Ability to give informed consent: Patients must be able to give informed consent or they will give assent with guardian consent.

Criteria for Exclusion of Participants:

1. Current rash consistent with acute cutaneous lupus (butterfly rash).
2. Contraindication to UVA1 phototherapy, including personal history of melanoma or non-melanoma skin cancer, history of other photosensitive disorders (e.g. porphyria cutanea tarda, polymorphous light eruption, xeroderma pigmentosum, etc.), or history of any type of organ transplant (solid organ or bone marrow).
3. Current use of frequently photosensitizing medication (e.g. tetracycline, doxycycline, isotretinoin).
4. Current or <2 months prior use of UVA1 phototherapy prior to enrollment.
5. Inability to receive UVA1 treatment safely and effectively (e.g. claustrophobia, wheelchair-bound, difficulty understanding instructions).
6. Nursing mothers, pregnant women, and women planning to become pregnant while on study are to be excluded.
7. Participants with a disease history deemed consistent with drug-induced lupus by study investigators.

5. STUDY PROCEDURES (See Appendix for Table of Study Visits)

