- Phototherapy orientation – The phototherapist will orient all patients to the safety protocols of the unit. Subjects will wear standard UV protective goggles and shield their genitals. A symptom questionnaire assessing symptoms of lupus flare, photosensitivity, and changes in medications will be provided at the initial phototherapy orientation. Participants will be asked to review this at home prior to each UVA1 treatment session. This questionnaire will also be reviewed at each UVA1 treatment session by the phototherapy nursing staff.
- Delivery of UVA1 phototherapy – Patients will receive UVA1 phototherapy according to the protocol stated in Table 1. **The time required to complete UVA1 treatment will be <30 minutes.**

Table 1. UVA1 Phototherapy Standard Protocol
1. Explain treatment to patient.
2. Patients should be treated three times per week.
3. Prior to each treatment session, review lupus flare and photosensitivity questionnaire.
4. Treat whole body except for genitals and “shielded cutaneous lupus lesion.”
5. Goggles should be worn at all times by the patient and the phototherapist.
6. Unit should be a fixed distance from patient. 
 • Whole body – 8-9 inches
7. Patient to apply sunscreen to nipple/areola and cover genitals.
8. Set unit to deliver appropriate dose ($\leq 20 \text{ J/cm}^2$).
9. Dose as follows: 
 a. Initial dose at 6 J/cm^2 b. Second dose at 12 J/cm^2 c. Third dose and all doses thereafter at 20 J/cm^2 in the absence of adverse effects
10. Prior to treatment, always review patient’s medications.

11. Prior to each treatment, inquire for any erythema or symptoms of lupus flare.
12. UVA1 light can induce HSV (cold sores) especially if patient has a personal history. If this occurs, notify the physician for treatment and possible prophylaxis.

Study Visit 2 –UVA1 Treatment Phase (Week 6, After 15 UVA1 Phototherapy Treatments)

The same assessment and procedures will be performed as in Study Visit 1 with the exception of informed consent, phototherapy orientation, and optional skin biopsies.

Study Visits 3 - End of UVA1 Treatment Phase (Week 11, After 30 UVA1 Phototherapy Treatments)

The same assessment and procedures will be performed as in Study Visit 1 with the exception of informed consent and phototherapy orientation.

Study Visit 4 - End of Observation Phase (Week 19, 8 Weeks After UVA1 Phototherapy Treatment Ends)

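### Section 12's no-dose-change rule for photosensitizing drugs does not except Exclusion 3 drugs, so a patient who starts one mid-course continues UVA1 at the same dose

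*Combined protocol and SAP*

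**What the plan says.** **At entry.** Section 4, Exclusion 3, keeps out patients with "Current use of frequently photosensitizing medication (e.g. tetracycline, doxycycline, isotretinoin"). The drugs are given as examples.

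**During treatment.** Section 12 calls for a medication review before UVA1 and then states that "no dose change will be instituted for photosensitizing medications, given the low dose of UVA1 in this study". The sentence does not mention Exclusion 3.

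**The per-session check.** Section 12 says: "A symptom questionnaire assessing symptoms of lupus flare, photosensitivity, and changes in medications will be provided at the initial phototherapy orientation". Nursing staff go over it before every session. Table 1, item 10 (Section 5), reads "Prior to treatment, always review", followed by a reference to the patient's medications and no further step.

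**What follows from the answers.** For flare, "suggestion of a lupus flare on the questionnaire will trigger immediate reporting to the PI prior to any further treatment". For photosensitivity, the PI is told and evaluates the patient; sunburn-type erythema lowers the dose to 6 J/cm², with withdrawal if symptoms persist. For a medication change, the only stated consequence is the no-dose-change rule.

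**Other relevant text.** Section 7 says that at return visits "subjects will update the investigators on changes to their disease history, associated symptoms, treatments". Those visits are Visit 2 ("Week 6, After 15 UVA1 Phototherapy Treatments") and Visit 3 ("Week 11, After 30 UVA1 Phototherapy Treatments"). Section 6 makes continued concomitant treatment conditional on the inclusion criteria and does not mention the exclusions. Its removal list covers missed treatments, flare and intolerance. The Appendix schedules the inclusion/exclusion review at Screening and Week 1 only.

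**The concern.** The protocol treats an Exclusion 3 drug as a reason not to give UVA1 to a new patient. Once treatment has begun, the same drug falls under a rule to leave the dose alone. Both provisions apply to the same 20 J/cm² regimen, so the low-dose rationale in Section 12 does not by itself explain why the drug matters at entry but not at, say, session 10.

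What is at stake is patient safety and uniform conduct. Section 11 lists erythema and photosensitive eruptions among the short-term risks. A nurse who learns of a new doxycycline prescription and follows the text gives the session at the planned dose. The information is collected in time to act on, but the protocol does not ask anyone to act before a reaction appears.

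**Working it through.** This is mainly a check of text against text, with a little schedule arithmetic.

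**1. The plan's own figure.** Section 18 gives 83% power for n = 12, difference 20%, SD 25%, one-sided alpha 0.05, one-sample t-test. The noncentrality is (20/25) × √12 = 2.77 on 11 degrees of freedom, and the exact power is 82.9%, which agrees. Recruitment is 12 / (1 − 0.20) = 15, a margin of 15 − 12 = 3 patients. The point does not depend on these figures; the margin matters only for the cost of the fix.

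**2. Tracing one case.** A patient reports before a session that doxycycline was started since the last one.

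| Provision | What it requires |
|---|---|
| Section 4, Exclusion 3 | Bars current use at entry; silent on later starts |
| Section 5, Table 1, item 10 | Review medications |
| Section 5, Table 1, item 9c | 20 J/cm² unless there are adverse effects; none yet |
| Section 12, questionnaire | Medication changes are covered; no report to the PI is required |
| Section 12, dose rule | No dose change |
| Section 6, concomitant therapy | Refers to the inclusion criteria, not the exclusions |
| Section 6, removal list | Does not include starting an excluded drug |
| Appendix | No repeat of the eligibility review after Week 1 |

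Following these provisions, the session goes ahead at the planned dose.

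**3. Length of the gap.** Inputs: 3 sessions per week for 10 weeks, so 3 × 10 = 30 sessions (Sections 5 and 6). Drug-course length is not in the documents; 1 to 2 weeks is assumed.
- 1 week: 1 × 3 = 3 sessions.
- 2 weeks: 2 × 3 = 6 sessions.

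Visit 2 follows session 15 and Visit 3 follows session 30. A course of this length can therefore begin and end between two visits. The outer bound is a drug started just after Visit 2 and taken to the end of treatment: sessions 16 to 30, which is 15 sessions or 15 / 3 = 5 weeks, with no scheduled investigator visit until treatment has finished. That bound requires continuous use and no reaction.

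**4. Size of a hold.** A one-week hold is 3 sessions, which equals the Section 6 removal threshold of 3 or more missed treatments. Section 5 reschedules sessions missed for reasons other than adverse events, but the protocol does not say whether a rescheduled session still counts as missed.

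**The case against.** The strongest reply is that the sponsor made a reasoned choice: Section 12 states a rule and gives the low UVA1 dose as its reason. Entry rules and on-study rules need not match. The word *frequently* in Exclusion 3 also allows a two-tier reading, in which Section 12 concerns only the weaker photosensitizers. There are safeguards at every session: nurses look for erythema, reactions go to a dermatologist or the PI, the dose can be cut to 6 J/cm², and full dose is conditional on there being no adverse effects. Nothing stops a nurse from raising a new drug with the PI.

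Much of this stands, and it rules out several stronger readings.
- *That Sections 4 and 12 contradict each other.* They do not: one governs entry and the other treatment, and the two-tier reading is available.
- *That the medication check leads to no rule at all.* It leads to one, which is to continue at the same dose.
- *That medications are reviewed only once, before the course, so that no rule covers later starts.* Table 1, item 10, and the per-session questionnaire make review before each session the natural reading.

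The two-tier reading is not written into Section 12, and staff applying the rule session by session should not have to infer it. The safeguards are real but act after a reaction. The low-dose rationale cannot simply be extended to Exclusion 3 drugs, because the protocol excludes users of those drugs at that same dose. If the sponsor does intend the extension, the text should say so.

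**Conclusion.** The point holds as a minor safety-conduct improvement that is cheap to make. As written, the Section 12 rule covers Exclusion 3 drugs started during treatment and directs staff to continue at an unchanged dose, with no required notice to the PI and no hold before a reaction.

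The gap lasts 3 to 6 sessions for an assumed 1- to 2-week drug course. A reader might multiply sessions by 20 J/cm² and take the total as a measure of harm. The documents do not support that: the total is the planned dose, with no excess exposure, and they give neither the frequency of new prescriptions nor the chance of a reaction. No event count can be claimed. A reader might also infer damage to the efficacy analysis, but the gap does not touch the endpoint or the stated power.

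The conclusion rests on reading the medication review as a per-session check and on taking Section 12 literally. An attentive PI or nurse may already act more cautiously than the text requires.

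**What to change.** 1. Limit the Section 12 sentence to photosensitizing drugs that Exclusion 3 does not cover.
2. Add to Section 12 and to Table 1, item 10: a newly started Exclusion 3 drug found at the pre-session review is reported to the PI before that session, and UVA1 is held until the PI decides. Substituting the drug or waiting out a short course is preferred; withdrawal is the last resort.
3. State that sessions held for this reason are rescheduled under Section 5 and do not count toward the missed-treatment removal rule in Section 6. Without this, a one-week hold could itself remove the patient.

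**Cost.** Two or three sentences and no new data collection, since medication changes are already covered before each session. In conduct, there is an occasional call to the PI and a delayed session. A hold may push Visit 3 past Week 11 by about its own length, and the room to extend is limited because treatment is confined to fall and winter. A rare withdrawal would draw on the three-patient margin, which Section 18 budgets for loss to follow-up and intolerance of UVA1; hence the preference for substitution or a short wait.

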13. PROCEDURES TO MAINTAIN CONFIDENTIALITY

Collection of samples:

A master file with the subject's demographic information (name, sex, race, age, contact information, birth date, diagnosis, medical record number, and surgical pathology number) will be developed, stored separately from the subject's samples and questionnaire data, and assigned a unique identification number. The identification numbers will be used to identify all samples collected during the course of the study. All information collected will be stored according to UT, FDA, and state guidelines, and all research utilizing subjects' samples must be approved by the IRB at UT Southwestern.

Storage of samples:

Each blood and skin biopsy sample will be stored in the UT Southwestern Department of Dermatology laboratory (NL8.110N) in a locked -80°C freezer with the subjects' unique identification number, a unique sample number, and date of collection. The samples stored will be under the supervision of the primary investigator and research associate(s). The samples will be stored until all test procedures have been completed, or until the samples are no longer considered viable. At the study closure, any remaining samples will be destroyed according to the UTSW laboratory policy and procedures. The subjects' identifiers will also be destroyed after final data analysis.

Linkage of sample to the donor subject:

The sample number will be linked to the database number in a separate log, and this link will not be broken throughout the course of the study.

Use of samples:

These samples will be used for a study within the Department of Dermatology by the PI ([name]) at UT Southwestern Medical Center.

Reports of DNA results:

Only the PI will receive the results of the DNA testing. The subject or their legally responsible representative, physician, family members, medical-insurance provider, life-insurance provider, and employer will *not* receive these results. The subject will give explicit, properly-informed written consent for the release of the DNA test results to the primary investigator as part of the consent process.

Approval of sample use:

The PI will be responsible for patient samples. No other investigator will receive samples.

Computer security:

The computer storing the donor-subject's identity is not linked to the internet and database access is password-protected.

Publication of private information:

Private information may be released to the investigator if the subject gives his/her consent/assent. No information will be published which would reveal the subject's identity.

Release of a donor-subject's sample to a third party for purposes other than research:

There are *no* conditions when a sample will be labeled with the patient's initials could be released to the donor-subject, family member, physician, insurance provider, or employer for any use.

Future contact with donor-subjects:

Subjects with cutaneous lupus will be invited to continue follow-up for future research participation. A subject's family members may be invited to participate in research if it is determined they have a history of cutaneous lupus. The subject will be given the investigator's contact information, and they will be invited by the proband to call the investigator to learn about the study.

Removal from the study:

A subject's sample and related data may be removed from the database if the subject chooses to no longer participate in the study, or has been incorrectly diagnosed with cutaneous lupus. Once enrolled in this study, the tissue and blood specimens will not be available for destruction or returned to the subject at their request.

